6.3 Measures to Minimise Bias: Randomisation and Blinding

6.3.1 Randomisation

Not applicable as this is a nonrandomised study.

6.3.2 Maintenance of Blinding

This is an open-label study therefore no procedures for blinding are applicable.

6.4 Study Intervention Administration/Accountability

Study intervention bottles and blisters will be brought back to the site and accountability performed. Accountability will be documented in the source documents and IWRS.

A record of the quantity of palovarotene dispensed to and administered by each participant must be maintained and reconciled with study intervention and accountability records.

Palovarotene status (treated or not treated) and regimen (chronic or flare-up or intercurrent flare-up or persistent flare up symptoms treatment) at the time of transition to Study CLIN-60120-452 will be collected at the Inclusion Visit.

6.5 Dose Modification

Participants will be instructed to contact study site personnel immediately in case of intolerable adverse reactions during palovarotene treatment. The investigator will assess the adverse reaction and, if appropriate, will instruct the participant to reduce the daily dose to the next lower dosage as shown in [Table 5](#); additional dose reduction should occur if adverse reactions continue to be intolerable. If the participant is already receiving the lowest possible dose, then consideration should be given to discontinue therapy temporarily or permanently or switching

to flare-up treatment only (see Section 6.1). Subsequent flare-up treatment should be initiated at the same reduced treatment that was tolerated previously.

Table 5 Dose Reduction of Palovarotene

Dose Prescribed	Reduced Dose
20 mg	15 mg
15 mg	12.5 mg
12.5 mg	10 mg
10 mg	7.5 mg
7.5 mg	5 mg
5 mg	2.5 mg
2.5 mg	1 mg

6.6 Continued Access to Study Intervention after the End of the Study

The aim of this rollover study is to provide continued access to treatment to participants who have completed one of the parent studies until palovarotene is reimbursed in the country where the study is being conducted, or another access programme becomes available, or until the study end date of November 2024 is reached, at which point the study will end. Therefore, participants will not receive any additional study intervention following the EOS.

6.7 Treatment of Overdose

For this study, any dose of palovarotene greater than those specified in Section 6.1 will be considered an overdose.

The sponsor does not recommend specific treatment for an overdose; any overdose should be treated with supportive care according to the signs and symptoms exhibited by the participant.

In the event of an overdose, the investigator/treating physician should:

- Contact the medical monitor immediately.
- Evaluate the participant to determine, in consultation with the medical monitor, whether study intervention should be interrupted or whether the dose should be reduced.
- Closely monitor the participant for any AE/SAE and laboratory abnormalities until palovarotene can no longer be detected systemically (at least 30 days).
- Document the quantity of the excess dose as well as the duration of the overdose. See Section 10.3.1 for reporting requirements concerning overdose.

6.8 Prior and Concomitant Therapy

The following medications are not allowed during palovarotene treatment (chronic or flare-up-based treatment):

- Vitamin A or beta carotene, multivitamins containing vitamin A or beta carotene, herbal preparations, or fish oil are not permitted from the day before the start of treatment until the last day of treatment.
- Synthetic oral retinoids other than palovarotene are not permitted in the 30 days prior to treatment until the last day of treatment.
- Concomitant use of tetracyclines and retinoids has been associated with benign intracranial hypertension. Therefore, use of tetracycline or tetracycline derivatives is prohibited during the study. If the participant experiences a medical condition that requires treatment with tetracycline and/or doxycycline, the study intervention should be discontinued for the duration of tetracycline treatment and the medical monitor should be notified. Prior to restarting treatment with palovarotene, an appropriate wash-out period of 3 days must be considered.

- Strong inhibitors of CYP450 3A4 are known to alter the metabolism of palovarotene. Thus, concurrent oral medications identified as strong inhibitors of CYP450 3A4 (see Section 10.5) are excluded. If during the study, the participant must take a strong inhibitor of CYP450 3A4, the study intervention is to be discontinued for the duration of treatment. Prior to restarting treatment with palovarotene, an appropriate wash-out period (five half-lives) must be considered (see Section 10.5).
- Strong inducers of CYP450 3A4 are also known to alter the metabolism of palovarotene. Thus, concurrent oral medications identified as strong inducers of CYP450 3A4 (see Section 10.5) are excluded. If during the study, the participant must take a strong inducer of CYP450 3A4, the study intervention may continue, but the medical monitor should be notified.
- Kinase inhibitors such as imatinib, and other drugs used off-label as potential treatments for FOP such as rapamycin, as reported in the literature. A washout period of 5 half-lives is required prior to enrolment into the study.

Prior medications will not be collected or recorded in the Study CLIN-60120-452 eCRF. These data will be transferred from the final parent study database and summarised at the Inclusion Visit.

Any medication (including over-the-counter or prescription medicines, recreational drugs, vitamins, herbal supplements and vaccines (e.g. COVID-19)) or other specific categories of interest that the participant receives during the study will be collected at the Inclusion Visit, the Follow-up Visits and the EOS/EW Visit along with:

- Reason for use;
- Dates of administration including start and end dates;
- Dosage information including dose and frequency.

The medical monitor should be contacted if there are any questions regarding concomitant or prior therapy.

The following data on concomitant procedures will be collected at the Inclusion Visit and at the Follow-up/EOS/EW Visits:

- Surgical procedure name;
- Indication;
- Reason for concomitant surgery;
- Date of surgery.

6.8.1 Preventive Medication

Assessment of 25-OH Vitamin D level is recommended and supplementation with Vitamin D for good bone health should be considered as per the ICC on FOP guideline [[ICC FOP 2022](#)] and local guidelines.

6.8.2 Rescue Medicine

Mucocutaneous toxicities are the most common side effects of systemic retinoids. The most frequently reported AEs during FOP clinical studies with palovarotene were primarily mucocutaneous in nature, including cheilitis/dry lips, dry skin, pruritus and alopecia, and were generally assessed as related to palovarotene.

Participants will be instructed to utilise symptomatic therapy (e.g. analgesics, skin emollients, lip moisturisers, artificial tears, or other helpful treatments), to minimize these side effects, or as prophylaxis in the studies.

Although palovarotene has not been proven to be phototoxic, precautionary measures for phototoxicity are recommended. Participants should avoid excessive exposure to sun and use protection from sunlight when it cannot be avoided (use of sunscreens, protective clothing, and use of sunglasses).

7 DISCONTINUATION OF STUDY INTERVENTION AND PARTICIPANT DISCONTINUATION/WITHDRAWAL

Discontinuation of specific sites or of the study as a whole are detailed in Section 10.1.9.

7.1 Discontinuation of Study Intervention

In rare instances, it may be necessary for a participant to permanently discontinue study intervention before the EOS. Palovarotene treatment for individual participants can be discontinued by the investigator if he/she believes the participants' safety is at risk. In the event of pregnancy, palovarotene treatment must be discontinued (Section 8.3.5).

If palovarotene is permanently discontinued, the participant will be withdrawn from the study. All reasonable efforts should be made by the study personnel to have the participants complete all study assessments of the EW Visit as per the SoA (see Table 1).

If palovarotene is permanently discontinued due to a safety concern, the participant will be monitored for safety (see Section 8.3.3 for follow-up of AEs/SAEs and Section 8.3.5 for follow-up of pregnancies).

7.1.1 Liver Chemistry Stopping Criteria

Not applicable to this study.

7.1.2 QTc Stopping Criteria

Not applicable to this study.

7.1.3 Treatment Interruption

Palovarotene can be temporarily discontinued if, after the daily dose of palovarotene has already been reduced to the lowest possible dose (see Section 6.5), the participant continues to experience intolerable adverse effects.

If palovarotene is temporarily interrupted, the participant will remain in the study and assessments performed as planned per the SoA.

If palovarotene is permanently discontinued, the participant will be withdrawn from the study and all reasonable efforts should be made by the study personnel to have the participant complete all study assessments of the EW Visit as per the SoA.

In case of suspected or confirmed COVID-19 (SARS-CoV-2) infection, the intervention administration may be temporarily discontinued depending on the participant clinical presentation. In some cases, the investigator may request a participant be retested before the intervention administration is resumed.

7.1.4 Rechallenge

If palovarotene is temporarily interrupted due to a safety related event, once the event resolves, treatment can resume at the discretion of the investigator. If the event reoccurs, palovarotene treatment may be temporarily interrupted again or permanently discontinued.

7.2 Participant Discontinuation/Withdrawal from the Study

- A participant may withdraw from the study at any time at his/her own request or may be withdrawn at any time at the discretion of the investigator for safety, behavioural or compliance reasons. Participants meeting exclusion criteria during the course of the study will be withdrawn.
- The legal guardian and the paediatric participant have the right to withdraw permission (consent or assent, respectively) at any time during the study. If the study staff identify any reluctance in the legal guardian or paediatric participant (e.g. signs of verbal or physical dissent) about continued participation in the study, the paediatric participant's

continuation in the study should be re-evaluated. The same principles that govern permission/assent/consent also govern its withdrawal. A participant will be withdrawn from the study if consent or assent if applicable (a paediatric participant's dissent should be respected) is withdrawn.

- At the time of discontinuing from the study, all reasonable efforts should be made by the study personnel to have the participants complete all study assessments of the EW Visit if possible, as shown in the SoA. See SoA ([Table 1](#)) for data to be collected at the time of study discontinuation and any evaluations that need to be completed.
- The reason for discontinuation will be recorded in the eCRF.
- The participant will be permanently discontinued from the study intervention and the study at that time.
- If the participant withdraws consent for disclosure of future information, the sponsor may retain and continue to use any data collected before such withdrawal of consent.
- If the participant requests to permanently discontinue the study intervention, they will be withdrawn from the study. In the case of ongoing AE/SAEs or pregnancy, they will be asked to be followed for safety (see Section [8.3.3](#) for follow-up of AEs/SAEs and Section [8.3.5](#) for follow-up of pregnancies).
- If the participant withdraws consent for any further contact, the investigator will explain in the medical records as to whether the withdrawal is only from further receipt of study intervention or also from study procedures and/or post-study intervention follow-up. This information must be entered in the eCRF.

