4.4 End of Study Definition

The EOS for an individual participant will be the date of study completion; the participant is considered to have completed the study if he/she has stopped study intervention due to palovarotene becoming reimbursed in the country where the study is being conducted, or another access programme becoming available, or the study end date of November 2024 being reached, whichever occurs first.

The EOS Visit can be an in-clinic visit or performed remotely and must take place before the participant transitions to commercial treatment.

Study end is defined as the date of last contact with the last participant in the study (Last Participant Last Visit (LPLV)).

Criteria for study intervention discontinuation and participant discontinuation/withdrawal from the study are described in Section 7.1 and Section 7.2, respectively. Loss to follow-up is described in Section 7.3.

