5.2 Exclusion Criteria

Participants will not be included in the study if any of the following criteria apply:

Medical conditions

1. History of allergy or hypersensitivity to retinoids, gelatin, lactose (note that lactose intolerance is not exclusionary) or palovarotene, or unresponsiveness to prior treatment with palovarotene.
2. Uncontrolled cardiovascular, hepatic, pulmonary, gastrointestinal, endocrine, metabolic, ophthalmologic, immunologic, psychiatric, or other significant disease.
3. Symptomatic vertebral fracture.
4. Any other medical condition/clinically significant abnormalities that would expose the participant to undue risk or interfere with study assessments.
5. Amylase or lipase $>2\times$ above the upper limit of normal (ULN) or with a history of chronic pancreatitis.
6. Elevated aspartate aminotransferase (AST) or alanine aminotransferase (ALT) $>2.5\times$ ULN.
7. Fasting triglycerides >400 mg/dL with or without therapy.
8. Suicidal ideation (type 4 or 5) or any suicidal behaviour at the Inclusion Visit as defined by the Columbia-Suicide Severity Rating Scale (C-SSRS).

Prior/concomitant therapy (see Section 6.8)

9. Current use of vitamin A or beta carotene, multivitamins containing vitamin A or beta carotene, or herbal preparations, fish oil, and unable or unwilling to discontinue use of these products during palovarotene treatment.
10. Exposure to synthetic oral retinoids other than palovarotene within 4 weeks of the Inclusion Visit.
11. Concurrent treatment with tetracycline or any tetracycline derivatives due to the potential increased risk of pseudotumor cerebri.
12. Use of concomitant medications that are strong inhibitors or inducers of cytochrome P450 (CYP450) 3A4 activity (see Section 6.8 and 10.5); or kinase inhibitors such as imatinib.

Other exclusion criteria

13. Palovarotene is reimbursed in the country where the study is being conducted.
14. Any reason that, in the opinion of the investigator, would lead to the inability of the participant and/or family to comply with the protocol.

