8.2.2 C-SSRS and Suicidal Ideation and Behaviour Risk Monitoring

Suicidal ideation and behaviour will be collected using the C-SSRS ('Baseline' version) at the Inclusion Visit for screening purposes. At Follow-up visits, the C-SSRS 'Since Last Visit' version will be used.

The adult form (designed for participants ≥ 12 years of age) will be used for all participants. Any participant reporting type 4 or 5 suicidal ideation or any suicidal behaviour within the past month prior to the Inclusion Visit, will not be eligible to participate in the study.

Although there was no treatment-related increase in suicidal ideation, suicidal behaviour or psychiatric disorders overall relative to untreated participants with FOP in clinical trials, depression, depression aggravated, anxiety, mood alterations and suicidal thoughts and behaviours have been reported in patients treated with systemic retinoids. In addition, there is a relatively high background prevalence (24%) of depression in untreated patients with FOP.

Therefore, participants being treated with palovarotene should be monitored appropriately and observed closely for suicidal ideation and behaviour or any other unusual changes in behaviour, especially at the beginning and end of the course of intervention, or at the time of dose changes, either increases or decreases. Participants who experience signs of suicidal ideation or behaviour should undergo a risk assessment. All factors contributing to suicidal ideation and behaviour should be evaluated and consideration should be given to discontinuation of the study intervention.

When informed consent or assent has been given, families and caregivers of participants being treated with palovarotene should be alerted about the need to monitor participants for the emergence of unusual changes in behaviour, as well as the emergence of suicidal ideation and behaviour and to report such symptoms immediately to the study investigator. Suicidal ideation and behaviour will be captured as an AE/SAE.

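### Protocol 7.2 requires permanent withdrawal for any exclusion criterion met on study, but 6.8 provides for interruption and restart, or continuation, with the drugs in criteria 11 and 12

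*Protocol*

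**What the plan says.** Protocol 7.2 first describes withdrawal as a matter of choice for the participant or the investigator. It then becomes mandatory: "Participants meeting exclusion criteria during the course of the study will be withdrawn". A later bullet in the same section gives the effect: "The participant will be permanently discontinued from the study intervention and the study at that time". No criterion is exempted, and the sentence points to no other section.

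Protocol 5.2 lists 14 exclusion criteria. Criterion 11 reads: "Concurrent treatment with tetracycline or any tetracycline derivatives due to the potential increased risk of pseudotumor cerebri". Criterion 12 covers strong CYP450 3A4 inhibitors, strong inducers and kinase inhibitors.

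Protocol 6.8 then says what to do if these drugs are needed during the study:

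- Tetracyclines: "the study intervention should be discontinued for the duration of tetracycline treatment". The medical monitor is told, and a 3-day wash-out is set before palovarotene is restarted.
- Strong CYP450 3A4 inhibitors: palovarotene is stopped while the inhibitor is taken, with a wash-out of five half-lives before restarting.
- Strong CYP450 3A4 inducers: "the study intervention may continue, but the medical monitor should be notified".

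Protocol 7.1.3 keeps a participant whose palovarotene is temporarily interrupted in the study, on the planned assessment schedule. Only permanent discontinuation leads to withdrawal there.

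**The concern.** Sections 7.2 and 6.8 give different outcomes for the same event. Section 6.8 plainly expects these drugs to be needed at times, because it describes the restart. A site that follows 6.8 breaches 7.2, and a site that follows 7.2 ignores 6.8.

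The study's primary purpose is to describe safety under continued treatment. If similar participants leave at some sites and stay at others, the time at risk and the disposition counts depend partly on which section a site happened to apply. The readers of the study report could not see that from the tables.

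**Working it through.** The protocol states no figure on this point, so the check is a comparison of text followed by a trace into the SAP.

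**Step 1: outcome under each rule.**

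| On-study event | Criterion (5.2) | Under 7.2 | Under 6.8 and 7.1.3 | Compatible? |
|---|---|---|---|---|
| Tetracycline needed | 11 | Withdrawn, permanently off treatment | Pause, wash-out, restart; stays in study | No |
| Strong 3A4 inhibitor needed | 12 | Same | Pause, wash-out, restart; stays in study | No |
| Strong 3A4 inducer needed | 12 | Same | Dosing may continue | No |
| Kinase inhibitor needed | 12 | Same | 6.8 prohibits it and gives no on-study exception | No conflict |

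The conflict therefore covers two of the 14 criteria, through three drug classes. The inducer row is the sharpest: continued dosing and permanent discontinuation cannot both hold.

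**Step 2: which outputs move.**

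- Disposition (SAP 5.2) counts completed participants, withdrawn participants and reasons for withdrawal. With 87 in the denominator, each participant handled differently moves a percentage by 1/87 = 1.1 points.
- Exposure (SAP 5.8.2.1) is last dose date minus first dose date plus 1. The TEAE window (SAP 5.7.2.2) closes 30 days after the last dose. Permanent withdrawal brings both forward.
- Study duration is the denominator of the flare-up rate (SAP 5.7.3.7) and of annualised healthcare use (SAP 5.7.3.5).
- Major deviations decide membership of the Per Protocol Set (SAP 4 and 5.3). Keeping a participant as 6.8 allows could be logged as a failure to withdraw under 7.2.

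**Step 3: follow-up at stake for one participant.** The documents give no event dates. As an illustration, assume a participant who would otherwise have reached Month 36, using the scheduled days in SAP 6.1:

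- event at Month 6: 1095 − 182 = 913 days lost if withdrawn
- event at Month 12: 1095 − 365 = 730 days lost
- event at Month 30: 1095 − 912 = 183 days lost

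These are upper values. A later entry or an earlier study exit makes them smaller.

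**The case against.** The best defence is that the specific rule governs the general one, so 6.8 would control these drugs and 7.2 would cover the rest. That is a sensible intention, but the protocol does not state it. Section 4.4 refers readers to 7.2 for withdrawal criteria, and Section 8 rules out waivers and exemptions, which invites a literal reading of 7.2.

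A second defence is that criterion 11 concerns concurrent use, so pausing palovarotene means the criterion is not met. Section 6.8, however, bars tetracyclines for the whole study and not only while palovarotene is being taken. The argument also cannot help with inducers, where dosing goes on.

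A third defence is that every analysis is descriptive. This stands: no test, error rate or sample size is affected.

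Several stronger readings are tempting, and the documents do not support them:

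- *Suicidality as a further contradiction.* Section 8.2.2 says "consideration should be given to discontinuation of the study intervention", which is softer than 7.2. But criterion 8 is tied to the Inclusion Visit, so a later event does not literally meet it.
- *Planned completers turned into withdrawals.* Criterion 13 reads "Palovarotene is reimbursed in the country where the study is being conducted", which taken alone would fall under 7.2. Section 4.4 answers this expressly: "the participant is considered to have completed the study if he/she has stopped study intervention due to palovarotene becoming reimbursed". What remains is an overlap in wording.
- *Most participants affected through reimbursement.* The documents give no split between reimbursement, another access programme and the November 2024 end date.
- *Safety follow-up cut short only for those withdrawn.* The 30-day period after the last dose applies to everyone (4.1), and persisting adverse events are followed until they resolve or stabilise, or the participant is lost to follow-up (8.3.1, 8.3.3).
- *A direct effect on TEAEs leading to withdrawal.* Taking a prohibited drug is not itself an adverse event. The illness being treated might be recorded as the cause, but the documents do not establish that.

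**Conclusion.** The contradiction between 7.2 and 6.8, supported by 7.1.3, is real for criteria 11 and 12 and should be corrected. It is an internal inconsistency that changes conduct, exposure time and the disposition table. The number of participants affected is unknown: anywhere from 0 to the maximum of 87, with nothing in the documents to narrow it.

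The conclusion rests on two readings. One is that the mandatory wording in 7.2 means what it says. The other is that the stay-in-study rule in 7.1.3 covers the pauses in 6.8. Section 7.1.3 opens with intolerable adverse effects, but its sentence on interrupted participants is not limited to them. Even without 7.1.3, the restart in 6.8 conflicts with permanent discontinuation.

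Reimbursement is a secondary wording matter only. No view is taken here on which clinical rule should stand.

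**What to change.** 1. Reconcile 7.2 with 6.8 and 7.1.3. State in 7.2 which exclusion criteria trigger withdrawal when met on study, and which are handled by their own section. The sponsor makes the clinical choice for each criterion.
2. Note in 7.2 that an exit because of reimbursement is classed as completion under 4.4, and carry the same rule into the disposition table in SAP 5.2.
3. Align the Protocol Deviation Plan, so that following the section that governs a criterion is not logged as a failure to withdraw.
4. Before database lock, use the concomitant medication records, which 6.8 requires with dates, to list participants who took a criterion 11 or 12 drug on study and whether each was withdrawn, interrupted or continued. This gives the count that is missing now.

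The cost is a short protocol clarification that goes through the criteria one by one, one disposition rule in the SAP, and one listing from data already collected. No new assessments or participants are needed.
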